4.3 Inclusion criteria

Each patient must meet all of the following inclusion criteria to be enrolled in the study:

4.3.1. Metastatic prostate carcinoma and at least one of the following:

4.3.1.1. Histologic diagnosis of small cell or neuroendocrine prostate cancer

4.3.1.2. Histologic diagnosis of prostate adenocarcinoma plus $\geq 50\%$ immunohistochemical staining for neuroendocrine markers (such as chromogranin, synaptophysin or neuron specific enolase)

4.3.1.3. Development of liver metastases in the absence of PSA progression as defined by PCWG2 criteria

4.3.1.4. Serum chromogranin A level $>5 \times$ upper limit of normal and/or serum neuron specific enolase (NSE) $>2 \times$ upper limit of normal

- 4.3.3. Patients with pure small cell neuroendocrine carcinoma on histology are not required to have received prior androgen deprivation therapy (ADT) or castrate levels of testosterone. Other patients are required to have surgical or ongoing chemical castration, with baseline testosterone level <50 ng/dL.
- 4.3.4. Patients capable of fathering children must agree to use an effective method of contraception for the duration of the trial and should continue use for 4 months after last dose of study drug
- 4.3.5. Subjects must be able to take oral medication and to maintain a fast as required for 2 hours before and 1 hour after MLN8237 administration.
- 4.3.6. ANC > 1500/mm³, platelets > 100,000/mm³, Hgb > 9 g/dL. Values must be obtained without need for myeloid growth factor or platelet transfusion support within 14 days, however, erythrocyte growth factor is allowed as per published ASCO guidelines.
- 4.3.7. Total bilirubin \leq ULN, SGOT (AST) and SGPT (ALT) < 1.5 x ULN. AST and/or ALT may be up to 5X ULN if with known liver metastases provided bilirubin is normal.
- 4.3.8. Adequate renal function as defined by serum creatinine \leq 1.5 x ULN. If creatinine >1.5 x ULN, calculated or measured creatinine clearance must be \geq 40 mL/minute (Cockcroft-Gault).
- 4.3.13. ECOG performance status 0-2
- 4.3.14. Estimated life expectancy > 3 months
- 4.3.15. Voluntary written informed consent before performance of any study-related procedure not part of normal medical care, with the understanding that consent may be withdrawn by the subject at any time without prejudice to future medical care.
- 4.3.16. Age >18 years

4.4. Exclusion criteria

Patients meeting any of the following exclusion criteria are ineligible for treatment in the study:

- 4.4.1 Radiation therapy to 25% of bone marrow within 2 weeks of first dose
- 4.4.2 Residual > Grade 2 toxicity from prior treatment must have resolved with the exception of those explicitly described elsewhere in entry criteria
- 4.4.3 Known history of uncontrolled sleep apnea syndrome and other conditions that could result in excessive daytime sleepiness, such as severe chronic obstructive pulmonary disease; requirement for supplemental oxygen.

- 4.4.4 Requirement for constant administration of proton pump inhibitor, H2 antagonist, or pancreatic enzymes. Intermittent uses of antacids or H2 antagonists are allowed (see section 5.5)
- 4.4.5 Severe or uncontrolled systemic infection
- 4.4.6 Myocardial infarction within 6 months prior to enrollment or has New York Heart Association (NYHA) Class III or IV heart failure, uncontrolled angina, severe uncontrolled ventricular arrhythmias, or electrocardiographic evidence of acute ischemia or active conduction system abnormalities. Prior to study entry, any ECG abnormality at Screening has to be documented by the investigator as not medically relevant.
- 4.4.7 Patient has received other investigational drugs with 14 days before enrollment
- 4.4.8 Serious medical or psychiatric illness likely to interfere with participation in this clinical study.
- 4.4.9 Other severe acute or chronic medical or psychiatric condition, including uncontrolled diabetes, malabsorption, resection of the pancreas or upper small bowel, requirement for pancreatic enzymes, any condition that would modify small bowel absorption of oral medications, or laboratory abnormality that may increase the risk associated with study participation or investigational product administration or may interfere with the interpretation of study results and, in the judgment of the investigator, would make the patient inappropriate for enrollment in this study.
- 4.4.10 Currently active other malignancy excluding controlled non-melanoma skin cancer. Patients are considered NOT to have “currently active” malignancy if they have completed any necessary therapy and are considered by their physician to be at less than 30% risk of relapse.
- 4.4.11 Treatment with the enzyme-inducing antiepileptic drugs phenytoin, carbamazepine or phenobarbital, or rifampin, rifabutin, rifapentine or St. John's wort within 14 days prior to the first dose of MLN8237 and during the study
- 4.4.12 Known history of human immunodeficiency virus (HIV) infection, hepatitis B, or hepatitis C. Testing is not required in the absence of clinical findings or suspicion.

4.5 Registration procedure

Patients will be centrally registered with the Weill Cornell Medical College (WCMC), Department of Medicine Clinical Trials Office. To register a patient, fax the following documents to the Clinical Trials

Office at [contact] AND email notification to [contact] or scan/email all documents to the email addresses listed above. Note that the study email address will not accept attachments > 5 MB, so large attachments should be split.

- WCMC Patient registration form
- First and last page of the fully executed informed consent form, plus additional pages if checkboxes for correlative studies are required.
- Fully executed HIPAA research authorization form (if separate from the consent document)
- Eligibility checklist signed and dated by investigator and research nurse
- Documentation of any eligibility waivers granted

In addition, entry of screening information into WCMC web-based system (REDCap) should be completed.

Central registration information is reviewed and entered into the HemOnc centralized research database. These documents should be emailed or faxed Monday to Friday from 9:00 AM to 4:45 PM EST. Patients will be assigned a sequence number for the protocol. The registering institution will then be faxed or emailed a copy of the sequence number as confirmation of a completed registration. Subjects should NOT receive any study medication prior to receipt of registration confirmation.

Registration of patients cannot occur until the Coordinating Center has received proper documentation from the registering institution of IRB approval, including a copy of the current approval letter, stamped consent and signed FDA Form 1572. These documents may be faxed to the Coordinating Center at [contact] or emailed to [contact]

4.6 Duration of follow-up. Patients will be followed every 3 months for up to 3 years. Following 3 years, patients will be followed yearly until death.

5. Patient Evaluation

5.1. Screening Period

The following procedures must be completed no more than 4 weeks from enrollment.

- Informed Consent
- Demographics
- Medical History
- Previous therapy
 - Surgical report
 - Radiotherapy report

- Previous systemic (hormonal, chemotherapy, other) therapy – drugs, doses, dates of therapy
- Complete Physical Exam including height and weight
- Vital Signs
- ECOG Performance Status
- Electrocardiogram
- CBC with differential and platelet count.
- Electrolytes, BUN, Creatinine, LDH,
- chromogranin A, neuron specific enolase
- Total protein, albumin, total bilirubin, AST, ALT, Alkaline phosphatase
 - Direct bilirubin is required for those patients with Gilbert's syndrome
- PSA
- Testosterone
- Consider coagulation profile if needed for biopsy
- Labs for research (up to 4 weeks prior to treatment)
- CT or MRI (abdomen-pelvis) plus CT of chest, within 4 weeks of treatment
- Bone scan, within 4 weeks of treatment
 - Any confirmatory tests to assess equivocal results of bone scan should also be completed within a month of enrollment
- Tumor tissue: archival tumor tissue must be requested at time of screening. Metastatic tumor biopsy is mandatory and may be completed at any time after informed consent prior to treatment (for research purposes only and results not needed prior to proceeding to therapy)

The following tests need to be performed with results within eligibility criteria range within 3 days of C1D1:

- CBC (absolute neutrophil count, hemoglobin, platelet count)
- Liver function tests (total bilirubin, AST, ALT, Alkaline phosphatase)

5.2 Treatment period

5.2.1 Cycle 1, Day 1

- Targeted Physical Examination with vital signs and weight
- ECOG Performance Status (PS)
- Adverse event evaluation
- Concomitant medications
- Concomitant procedures
- Up to 3 days prior to treatment the following labs will be performed:
 - CBC with differential and platelet count
 - Electrolytes, BUN, Creatinine
 - Total protein, albumin, total bilirubin, AST, ALT, Alkaline phosphatase, Lactate dehydrogenase (LDH), uric acid
 - Serum level of chromogranin A, neuron specific enolase, carcinoembryonic acid (to be performed centrally)
 - CTC count (CellSearch methodology, accepted up to 4 weeks prior to treatment, to be performed locally)—optional
 - PSA, Plasma and PBMC for research (or within one month prior to treatment, to be performed centrally)—Do not need to perform if done at screening
 - Administration of MLN8237

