12.3.2 Serum marker response (PSA, chromogranin, neuron specific enolase)

Serum PSA, chromogranin, and neuron specific enolase (NSE) responses are determined by comparing the nadir level after therapy to the baseline, pre-treatment level determined just prior to initiating therapy. Declines of $\geq 30\%$ and 50% , confirmed by a value ≥ 2 weeks later, will be reported. Serum marker progression will be defined as a rise of $> 25\%$ above either the pretreatment level or the nadir level (whichever is lowest). PSA must increase by > 2 ng/ml to be considered progression. Confirmation requires a second consecutive rising PSA, chromogranin, or NSE at least 2 weeks apart. Marker stabilization is referred to as any set of values that do not meet the criteria for response or PSA progression.

12.3.3 CTC count response (CellSearch). Baseline CTC counts of < 5 when measured by CellSearch methodology have been associated with better prognosis (overall survival).[34, 35] In addition, changes in CTC counts after initial therapy have been demonstrated to be predictive.[36] We will explore the prognostic and predictive significance of 4 groups as has been described:

Baseline < 5 , follow up < 5
Baseline ≥ 5 , follow up < 5
Baseline < 5 , follow up ≥ 5
Baseline ≥ 5 , follow up ≥ 5

In addition, we will report individual subject's CTC count change from baseline.

13.0 Data Collection The data collection plan for this study is to utilize a study-specific (WCMC CTSC-supported) REDCap database to capture all treatment, toxicity, and efficacy data for all enrolled patients.

13.1 Confidentiality In order to protect confidentiality of the data, patient full names will be removed and data coded with patient initials and study subject numbers. All primary data will be kept in locked file cabinets or password-protected computers and available only to the investigators and appropriate regulatory personnel (e.g., IRB, FDA, etc.).

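### Section 5.2.1 lets a PSA up to a month old replace the Cycle 1 Day 1 PSA, contradicting the baseline in 12.3.2; where PSA is rising before treatment, PSA decline is understated

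*Protocol*

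**What the plan says.** Section 5.2.1 opens its C1D1 laboratory list with a short window: "Up to 3 days prior to treatment the following labs will be performed". Chromogranin A and NSE sit under that window with no exception. PSA does not. It shares a line with the research blood, "PSA, Plasma and PBMC for research (or within one month prior to treatment, to be performed centrally", and the line ends with a waiver: "Do not need to perform if done at screening".

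PSA is on the screening list in section 5.1 for every patient. That list is timed to enrollment: "The following procedures must be completed no more than 4 weeks from enrollment".

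Section 12.3.2 gives PSA, chromogranin and NSE one response definition: "responses are determined by comparing the nadir level after therapy to the baseline, pre-treatment level determined just prior to initiating therapy". Declines of at least 30% and 50% count when "confirmed by a value ≥ 2 weeks later, will be reported". Marker progression is a rise of more than 25% "above either the pretreatment level or the nadir level (whichever is lowest"). For PSA the rise must also exceed 2 ng/ml, and a second consecutive rising value at least 2 weeks apart must confirm it.

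The study calendar marks PSA at both Screening and C1D1, with no footnote on PSA. Section 1.4 has PSA drawn on day 1 of every cycle. PSA response rate is a secondary objective (section 2.2).

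**The concern.** A site that follows 5.2.1 to the letter may hold no PSA value that meets 12.3.2, and a missed pre-dose draw cannot be recovered later. Because screening PSA is mandatory, the waiver is open to every patient. The three markers then share one baseline definition but not one baseline age: up to 3 days for chromogranin A and NSE, up to a month for PSA.

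The age matters when PSA moves between the two dates. In a patient whose PSA is climbing, the screening value is lower than the level at which treatment began. A real decline is then measured from too low a start and can miss the 30% or 50% cut-off. Growth that took place before the first dose can also count toward the 25% rise that defines marker progression.

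**Working it through.** **Side by side.** Section 12.3.2, the calendar and section 1.4 all point to a PSA on day 1 or immediately before therapy. The waiver line in 5.2.1 alone departs from them. This contradiction needs no assumption.

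**Plan's own figure.** There is none to reproduce: no sample size, power or error rate in the protocol uses the PSA baseline.

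**Inputs.** The cut-offs (30%, 50%, 25%, 2 ng/ml) come from 12.3.2. The 3-day and one-month windows come from 5.2.1. The lag is taken as 28 days, near the upper end of what 5.2.1 allows. The protocol gives no PSA doubling time, so 1 to 12 months is assumed (30.4 days per month), with stable and falling PSA alongside.

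**Formulas.** Assume exponential change.
- Ratio of the C1D1 PSA to the screening PSA: k = 2^(lag / doubling time).
- A true fall d from C1D1 is recorded as 1 − (1 − d)k.
- The true fall needed to record 50% is 1 − 0.5/k.
- The change from C1D1 at which PSA is 25% above the screening value is 1.25/k − 1.

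Example at 3 months: k = 2^(28/91.2) = 1.237. A true 50% fall reads as 1 − 0.5 × 1.237 = 38.1%. The fall needed is 1 − 0.5/1.237 = 59.6%.

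| Assumed PSA course, 28-day lag | k | True 50% fall reads as | True fall needed to read 50% | Change from C1D1 that reaches +25% |
|---|---|---|---|---|
| Doubling in 1 month | 1.893 | 5.3% | 73.6% | −34.0% |
| Doubling in 2 months | 1.376 | 31.2% | 63.7% | −9.2% |
| Doubling in 3 months | 1.237 | 38.1% | 59.6% | +1.0% |
| Doubling in 6 months | 1.112 | 44.4% | 55.0% | +12.4% |
| Doubling in 12 months | 1.055 | 47.3% | 52.6% | +18.5% |
| Stable | 1 | 50% | 50% | +25% |
| Halving in 3 months | 0.808 | 59.6% | 38.1% | +54.6% |

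**Shorter lag.** At 14 days, a true 50% fall reads as 31.2%, 41.3%, 44.4%, 47.3% and 48.7% for the five doubling times.

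**Progression.** PSA that has not changed since C1D1 is already more than 25% above the screening value if the doubling time is below 28 × ln 2 / ln 1.25 = 87.0 days (93.2 days for a 30-day lag). This is not yet progression under 12.3.2:
- The reference is the lower of pretreatment level and nadir. At a 3-month doubling time, any fall from C1D1 of more than 1 − 1/1.237 = 19.2% puts the nadir below the screening value, and the screening value then plays no part.
- The rise must exceed 2 ng/ml. For an unchanged PSA at a 2-month doubling time, that needs a screening value above 2/0.376 = 5.3 ng/ml.
- A second consecutive rising value is required, so a PSA that stays flat after C1D1 is not confirmed.

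**With a 3-day baseline.** A true 50% fall reads as 46.5%, 48.3%, 48.8%, 49.4% and 49.7% for the five doubling times. Most of the distortion is gone.

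**The case against.** The strongest defense is that the waiver was meant for the research blood only. Sections 5.1 and 6.2 give research samples a four-week allowance, while the calendar and 1.4 keep PSA on day 1 without exception. PSA may simply have been swept into the same line. That is plausible, but the printed line includes PSA and sites will follow it. If this reading is right, it argues for the correction.

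A reader might infer that the trial's PSA response rate is biased downward as a whole. The protocol does not support that. It nowhere says that PSA is rising before treatment. Section 12.3 notes that NEPC often does not secrete PSA, and entry route 4.3.1.3 requires that PSA has not progressed. A rising PSA cannot be excluded either: the trial also covers castrate-resistant disease, and entry through serum chromogranin or NSE (4.3.1.4) sets no PSA condition. The bias is therefore conditional, and its share of patients is unknown.

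A reader might also infer that the baseline could be well over a month old, because the general screening window runs to enrollment and not to first dose. The waiver line itself states a one-month limit before treatment, so an older value follows only if the screening clause is read apart from that limit.

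The objection that the reach is small stands. PSA progression does not count as progressive disease (protocol summary, secondary endpoints), and PSA response is one of several secondary endpoints.

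**Conclusion.** The contradiction between 5.2.1 and 12.3.2, the calendar and 1.4 is established from the text. Its effect on PSA response is conditional. With a rising PSA and a 28-day-old baseline, a true 50% fall is recorded as about 5% to 47% across assumed doubling times of 1 to 12 months, and so misses the 50% cut-off. There is no bias if PSA is stable, and it reverses if PSA is falling. These sizes rest on assumed exponential growth, assumed doubling times and a lag near the maximum; shorter lags give less.

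Marker progression can be overstated only when no later nadir lies below the screening value and the 2 ng/ml and confirmation conditions are also met. The primary radiographic endpoint, its decision rule and the sample size do not depend on PSA and are unaffected. The point is worth correcting because it touches a listed secondary endpoint and the remedy is small.

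**What to change.** Three wording changes:
- In 5.2.1, take PSA off the research-blood line and list it with chromogranin A and NSE among the C1D1 labs drawn up to 3 days before treatment, without the screening waiver. The 3-day figure comes from the 5.2.1 list. The calendar's own 3-day footnotes cover only CBC and chemistry, and 12.3.2 gives no number of days.
- Keep the one-month allowance for both research plasma and PBMC. Restricting it to PBMC would put 5.2.1 in conflict with 6.2, which grants it to both.
- In 12.3.2, state that the C1D1 draw is the PSA baseline.

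The cost is one additional PSA assay per patient, on blood already being drawn at C1D1.

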5.2.3 Cycle 1, Days 2-7

- Administration of MLN8237

5.2.4 Cycle 1, Day 8 (Visit window +/- 3 days)

- Targeted Physical Examination with vital signs and weight
- ECOG PS
- Adverse event evaluation
- Concomitant medications
- Concomitant procedures
- Up to 3 days prior to C1D8 the following labs will be performed:
 - CBC with differential and platelet count
 - Electrolytes, BUN, Creatinine

- Total protein, albumin, total bilirubin, AST, ALT, Alkaline phosphatase, Lactate dehydrogenase (LDH), uric acid
- Blood for research (central)

5.2.5 Cycle 1, Day 15 (Visit window +/- 3 days)

- Targeted Physical Examination with vital signs and weight
- ECOG PS
- Adverse event evaluation
- Concomitant medications
- Concomitant procedures
- Up to 3 days prior to C1D15 the following labs will be performed:
 - CBC with differential and platelet count
 - Electrolytes, BUN, Creatinine
 - Total protein, albumin, total bilirubin, AST, ALT, Alkaline phosphatase

5.2.6 Day 1 treatment days of subsequent cycles (cycle 2 and beyond – see specifics for C3D1 below) Visit window +/- 3 days. Laboratory evaluation for determination of study drug dosing (e.g. CBC and chemistry) may be performed up to 3 days prior to treatment.

- Targeted Physical Examination with vital signs and weight
- ECOG Performance Status assessment
- CBC with differential and platelet count
- Electrolytes, BUN, Creatinine
- Total protein, albumin, total bilirubin, AST, ALT, Alkaline phosphatase, Lactate dehydrogenase (LDH), uric acid
- PSA
- Chromogranin A, neuron specific enolase (central labs)
- Adverse event evaluation
- Concomitant medications
- Concomitant procedures
- Administration of MLN8237

5.2.6.1 Cycle 3, Day 1 (Visit window +/- 3 days)

Follow protocol procedures for D1 of subsequent cycles AND:

- CTC count (CellSearch, performed locally)- optional

5.2.7. Days 2-7 treatment days of subsequent cycles (cycle 2 and beyond)

- Administration of MLN8237

5.2.8 Day 8 of subsequent cycles (cycle 2 and beyond)- (Visit window +/- 3 days)

- Adverse event evaluation
- Targeted Physical Examination with vital signs and weight
- ECOG PS
- Up to 3 days prior to D8 the following labs will be performed:
 - CBC with differential and platelet count
 - Electrolytes, BUN, Creatinine
 - Total protein, albumin, total bilirubin, AST, ALT, LDH, Alkaline phosphatase,

5.2.9 Day 15 of subsequent cycles (cycle 2 and beyond)

- Evaluation of subjects on D15 of each cycle (except cycle 1) is at the discretion of the investigator

5.2.10 Radiographic evaluation – See Section 7.0

To be performed after cycle 3, and following every 3rd subsequent cycle, or as clinically indicated.

Consideration should be made for confirmatory scans after 4 weeks should criteria for PR or CR by RECIST be met at any imaging time point.

5.2.11 At progression

- Targeted Physical Examination with vital signs and weight
- Adverse event evaluation
- ECOG Performance Status

- PSA
- CBC with differential and platelet count
- Electrolytes, BUN, Creatinine
- Total protein, albumin, total bilirubin, AST, ALT, Alkaline phosphatase, Lactate dehydrogenase (LDH), uric acid
- Serum level of chromogranin A, neuron specific enolase, carcinoembryonic acid- central labs (can be performed at progression or end of study)
- CTC count (CellSearch)- optional
- Blood for research
- Optional metastatic tumor biopsy for research
- CT or MRI (abdomen-pelvis) plus CT of chest within 2 weeks of progression visit
- Bone scan

5.2.12 End of study (must occur > 30 days after last dose of study drug; research lab procedures performed as part of progression visit do not need to be repeated).

- Targeted Physical Examination with vital signs and weight
- Adverse event evaluation
- ECOG Performance Status
- PSA
- CBC with differential and platelet count
- Electrolytes, BUN, Creatinine
- Total protein, albumin, total bilirubin, AST, ALT, Alkaline phosphatase, Lactate dehydrogenase (LDH), uric acid
- Serum level of chromogranin A, neuron specific enolase, carcinoembryonic acid- central labs (can be performed at progression or end of study)
- CTC count (CellSearch) - optional
- Blood for research (can be performed at progression or end of study)

Standard lab evaluations (including CBC, chemistry exams) may be performed at approved CLIA certified local laboratories with the investigator's pre-approval.

5.2.13 Long term follow up

Subjects should be followed for survival every 3 months for up to 3 years following end of study visit (in-office visits at study institutions are not necessary)

